64 women will be recruited from the practices of gynecologists and their colleagues. Inclusion criteria will include being sexually active (either with partner or self), post-menopausal, (without spontaneous menses for at least one year, a non-estrogenized vaginal maturation index and a vaginal pH >4.6); experiencing at least 3 months duration with, at least, significant pain on the Numerical Rating Scale (NRS) 0-10-point scale (0-no pain, 1-3 mild, 4-6-moderate, 7-9-significant, 10-severe pain) from secondary provoked vestibulodynia (SPVD). The pain must be significant enough to cause them distress as measured by Female Sexual Distress Scale-Revised (FSDS-R). A score of ≥ 11 effectively discriminates between women with Female Sexual Distress and no FSD. The pain must be significant enough to affect their sexual function, Female Sexual Function Index (FSFI) with a score of 26 or less and effect their sexual activities noted weekly with the standard Sexual Activities Log (SAL).

The intake pelvic examination, including of the vagina, will be normal for a woman's age and years since menopause.

Subjects may or may not have points of erythema in the vulvar vestibule as is common in women suffering from provoked secondary vestibulodynia.

A subject to be included in the study, must have at least significant (7) or above on the Numeric Rating Scale (NRS) of pain intensity (NRS) during the Q-tip test performed at the initial screening visit. Whereas, the Q-tip test must elicit at least significant pain intensity, visible erythema is not necessary to be included in the study. The descriptive characteristics of the pain will be documented using the standard Vulvovaginal Symptoms Questionnaire (VVSQ).

Inclusion Criteria:

Generally healthy women must meet the following eligibility criteria:

1. For surgically menopausal women, be 20-70 years of age and at least 12 months post menopause.
2. For naturally postmenopausal women, be 40-70 years of age and at least 1 year post menopause (defined as no spontaneous menses for 1 year).
3. In screening their vaginal pH will be 4.6 or greater and their vaginal maturation index will be consistent with vaginal atrophy. Vaginal atrophy is thinning, drying and of the vaginal walls due to having less estrogen in the body.

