Examination: The intake pelvic examination, including of the vulva and vagina, will be normal for a woman's age and years since menopause.

Documentation of Erythema: At each visit, erythema of the vestibule will be noted as "present" or "not present" and its location and that of the Q-tip induced pain entered as a drawing on the study chart, see below. There will be no photographic documentation of subjects.

The Q-tip test will be performed at the initial screening visit and all subsequent clinic visits (week 0, 2 , 4). The Q-tip test is a standardized test and involves palpating the vulvar vestibule with a soft, cotton wool-tipped stick and noting the existence of any pain, its location and intensity. Documentation is then made of both the location and intensity of any pain. The intensity of the pain is rated using a standard Numeric Rating Scale (NRS) of pain intensity where. (0) is no pain; (1-3) is mild pain; (4-6) is moderate pain (7-9) is significant pain and (10) is severe pain. Upon initial screening the pain intensity must be at least 7 (significant).

Documentation of sites of elicited or provoked pain will be noted on a clock face standardized clock face diagrammatic drawing with 6 o'clock being at the center of the posterior fourchette of the vulvar vestibule.

Assessment of vaginal atrophy: The Vaginal Maturation Index and Vaginal pH together will be used to establish the lack of estrogenic effect on the vaginal epithelium. Weber MA¹, Limpens J, Roovers JP Assessment of vaginal atrophy: a review Int Urogynecol J. 2015 Jan;26(1):15-28. . Tucker KM, Godha, Mirkin Archer DF Vaginal pH: a simple assessment highly correlated with vaginal morphology and symptoms in postmenopausal women Menopause. 2018 Mar 5.

Vaginal Maturation Index: Vaginal smears will be taken from the upper one third of the lateral vaginal wall for the Vaginal Maturation Index. The Vaginal Maturation Index quantifies the relative proportion of the vaginal parabasal (P), intermediate (I), and superficial (S) cells presented as % P / % I / % S. Vulvovaginal atrophy or estrogen deficiency will be demonstrated by a high percentage of parabasal cells, some intermediate cells and a paucity of superficial cells.

Vaginal pH: Vaginal pH > 4.6 as indication of atrophy, in the absence of infection or semen, of the vaginal epithelium using standard pH paper. Subjects will be asked not to have intercourse with semen deposited in the vagina 24 hours prior to their clinic study visit.

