- Apply the ointment once a day; if any irritation occurs stop using the ointment and notify your clinical trial gynecologist Do not restart to use the ointment until your irritation completely resolves. You will then be instructed to reduce the frequency of application to twice per week or less depending on your discussion with and instructions from your clinical trial gynecologist .
- Do not wash off the ointment from the treated area before the next application. When you wash the treatment area or bathe, apply the ointment afterwards, not before.
- Treatment with the ointment should be continued for a total of 4 weeks as instructed by your clinical trial gynecologist.. You will be seen at regular intervals during this time period by your clinical trial gynecologist.

•The ointment is not a cure for any condition and your condition may reoccur during or after treatment and may need further treatment.

What should I avoid while using catechins ointment?

- Do not apply the ointment on open wounds.
- While being treated with the ointment, and you do choose to have sexual contact, (genital, anal or oral) note that the ointment may weaken condoms and vaginal diaphragms therefore you must wash off the ointment carefully before having protected sexual contact. Talk to your doctor about safe sex practices.
- Avoid contact with your eyes, nostrils and mouth while ointment is on your finger(s).
- Do not expose the genital area treated with the ointment to sunlight, sunlamps or tanning beds.
- Do not cover the treated area. Loose-fitting undergarments can be worn after the ointment

PLEASE NOTE• The ointment is naturally a light reddish-tan color and therefore may stain your light-colored clothes and bedding. It is recommended to wear darker colored undergarments or an unscented disposable cotton panty liner while using the ointment.

How should I store catechins ointment?

- Store the ointment refrigerated or up to 77°F (25°C). • Do not freeze the ointment.
- Make sure the cap on the tube is tightly closed.
- Bring the tube of the ointment when you come to your scheduled clinic study visits.

Keep all medicines out of the reach of children. Do not give the ointment to other people, even if they have the same symptoms.

All subsequent visit dates for the treatment period will be calculated from Week 0 (Visit 1) date.

Week 2 (Visit 2)

The following procedures will be performed at the study clinic at the end of Week 2:

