Distribution of new copies of the SAL, FSFI, NRS, VVSQ, FSDQ-R, a question about any change in medications, along with self-addressed envelopes which will be labeled with the patient number for their return to the Investigator. Instructions will be given to complete the questionnaires at the conclusion of week 6 .

Alternatively, subject will be filling out questionnaires on secure, HIPAA compliant, website.

Consent Protocol:

Subjects will be given a written description of the study and possible untoward effects of the protocol. They will sign the IRB-approved informed consent.

Accepted subjects will be randomized and only a non-participant in the clinical trial will hold the code. Except for subjects who are excused from the trial prior to its completion because of any adverse reaction (i.e. irritation) the code will not be broken prior to the completion of the last subject's protocol.

Subjects will be consented at the initial study visit by the clinical trial gynecologist.. The clinical trial gynecologist will be available for consent discussion.

The Study Treatment: Drugs – The 10% GTO (10% 7.5% sinecatechins ointment, diluted Veregen ®) in petrolatum ointment will be furnished by Town Total Compounding Center Pharmacy ([name]), at week 0, in numbered, but otherwise unmarked compressible opaque, 15 gram tubes that will be examined at each visit. The placebo will be petrolatum ointment with an inert vegetable dye to visually appear the same as the drug. Subjects will be instructed to bring in their tubes at their 2 and 4 -week visits. The subjects will be instructed in the application of one ½ inch strand of either the study drug: 10% (diluted Veregen) or placebo once daily to the vulvar vestibule. Application – Subjects will be instructed to apply a ½ inch strand, lightly to painful or reddened areas of the vulvar vestibule. This is done daily for four weeks. Subjects will apply with a fingertip, taking care to avoid placing it into the vagina. (detailed instructions provided in this document) .

Compliance: At each visit the tubes will be weighed.

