The study medication and placebo have a red brown color and may therefore stain underwear. Subjects will be advised to wear panty liners every day that they apply the study medication in order to avoid staining of their underwear with the medication or placebo.

7. Monitoring and Reporting of Adverse Events/Serious Adverse Events: During the study, if you experience any medical problems, suffer a research-related injury, or have questions, concerns or complaints about the study, please contact your clinical trial gynecologist. If you seek emergency care, or hospitalization is required, alert the treating physician that you are participating in a research study being conducted by your clinical trial gynecologist.

Monitoring of Adverse Events will be done by patients reporting any adverse event to their clinical trial gynecologist. No serious adverse events are expected.

8. Study Oversight: In the unlikely event of the need to prematurely terminate this study of 10% , [name] will be the one to decide to terminate the study. The study will be made available for monitoring, auditing, IRB review and regulatory inspection by providing direct access to study related source data.

9. Data Management- Preliminary Power Analyses and Sample Size Estimates

Power Analyses

For Primary Outcome: Pain Score:

Sample size was calculated to achieve at least 80% power with a significance level of 0.05 using a two-tailed, two-sample t test. A sample size of 56 subjects (28 subjects in treatment group and 28 subjects in the placebo group) was estimated to achieve 80% power to detect at least 2.0-points mean difference between treatment and placebo groups. The Initiative on Methods, Measurement, and Pain Assessment in Clinical Trials suggests that reductions in pain intensity of at least 15–20%, or 2 points in the 0–10 scale, reflect clinically important changes (Dvorkin et al, Core Outcome Measures for Chronic Pain Clinical Trials:

IMMPACT Recommendations Pain: 2005 Jan; 113 (1-2) pp: 9-19)). The pain classification on a 0-10 scale will be as follows: 0 no pain; 1-3 mild pain; 4-6 moderate pain; 7-9 significant pain; 10 severe pain. To compensate for possible withdrawal of 15% of patients in the vulvodynia study, a total sample size of 64 participants (32 in the treatment group, 32 in the placebo group) will be required.

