The power analyses were based on previous research data on the effectiveness of the off label use of dilute Veregen (5% sinecatechins ointment) green tea extract (GTE) for the treatment of significant to severe vulvar pain (Patent US 2016/0271102 A1).

Statistical Analyses

Participants randomized to the dilute Veregen (10% sinecatechins ointment) green tea extract (GTE) arm will be compared to those randomized to placebo arm on demographic, descriptive and clinical variables at baseline using chi-square analysis for categorical variables, Student t test and ANOVA test for parametric data and Mann-Whitney U test for nonparametric data.

The ordinal variables (scores from the FSFI, Sexual Distress Scale revised, and the Sexual Activity Log questionnaires) will be analyzed using ANOVA test.

The nominal variables (binary categories from the Vulvovaginal Symptom Questionnaire, Erythema presence/absence and the Sexual Activities Log) will be analyzed using chi-square test. The p-values of less than 0.05 will be considered as statistically significant. These measures will be analyzed at the following assessment points (baseline, 2-week visit, 4-week visit, and 6-week follow-up).

10. IRB Review/Ethics/Informed Consent: Please see attached Informed Consent Document submitted.

IRB Review/Ethics/Informed Consent

This study will be conducted in accordance with the ethical principles that have their origin in the Declaration of Helsinki and that are consistent with Good Clinical Practice and applicable regulatory requirements. The study will be conducted in accordance with the regulations of the United States Food and Drug Administration (FDA) as described in 21 CFR 50 and 56 [add 312 for IND studies or 812 for device studies], applicable laws and the IRB requirements.

The Sponsor will submit any change to the protocol to the IRB for review and approval before implementation. A protocol change intended to eliminate an apparent immediate hazard to subjects will be implemented immediately provided the FDA and the reviewing IRB are notified within 10 working days.

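### Women come from several practices, but the pain comparison is unwritten and no analysis has a practice term: a modest loss of precision, cheaply avoided, if more than one practice scores pain

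*Combined protocol and SAP*

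**What the plan says.** - **Recruitment.** Section 4: "64 women will be recruited from the practices of gynecologists and their colleagues". The number of practices, study clinics and examiners is not given.
- **Who examines.** Study Related Procedures in the synopsis names the trial gynecologist together with medical assistants. The ointment instruction sheet in Section 5 tells the woman: "You will be seen at regular intervals during this time period by your clinical trial gynecologist".
- **Q-tip test.** Section 5 says that it "involves palpating the vulvar vestibule with a soft, cotton wool-tipped stick". Pain is rated 0 to 10 at screening and at weeks 0, 2 and 4, and a rating of at least 7 is needed for entry. The test is called standardized, but no pressure, calibration or examiner training is described.
- **A second pain rating.** The synopsis also has a weekly self-rated diary on the same scale, and the visit schedule lists pain level on a separate row from the Q-tip test.
- **Allocation.** "Accepted subjects will be randomized and only a non-participant in the clinical trial will hold the code". Medication is obtained through the IVRS. Nothing is said about blocks or strata, either way.
- **Pain analysis.** Section 9, Power Analyses: "Sample size was calculated to achieve at least 80% power with a significance level of 0.05 using a two-tailed, two-sample t test". The 28 women per arm "was estimated to achieve 80% power to detect at least 2.0-points mean difference between treatment and placebo groups". The outcome is labelled only as a pain score and is not tied to the Q-tip or the diary rating.
- **Other analyses.** Section 9, Statistical Analyses, gives t test, ANOVA and Mann-Whitney for baseline comparisons, ANOVA for the questionnaire scores and chi-square for binary items. Pain after baseline is not listed.

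**The concern.** A cotton-tipped stick pressed by hand gives a stimulus that depends on who presses it. If several practices examine women, some of the spread in Q-tip ratings belongs to the examiner rather than to the woman. Case mix may differ between practices as well. The one test the plan links to pain makes no allowance for either, so that spread would be counted as noise. With 28 evaluable women per arm there is little precision to spare.

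Because the pain analysis is still unwritten, a practice term costs almost nothing now. If it were chosen after unblinding, it would be open to the charge of being picked for its result.

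**Working it through.** **Inputs.** From Section 9: two-sided 0.05, 80% power, difference 2.0, 28 per arm. Not in the documents, so assumed: the SD, the number of practices (2 to 8, equal in size), and the ICC, meaning the share of pain variance lying between practices (0 to 0.20).

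**1. The plan's own figure.** With no SD stated, 56 cannot be reproduced directly, so I solved backwards. For a t test on 54 df the noncentrality is δ/(σ√(2/n)). With σ = 2.62 it is 2.0/(2.62 × √(2/28)) = 2.0/0.700 = 2.86, which gives 80% power. The normal approximation gives σ = 2.67. I use 2.62 as the total SD.

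**2. What a practice term can remove.** With arms balanced within practice, the residual SD is 2.62 × √(1 − ICC):

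| ICC | Residual SD | Power with a practice term |
|---|---|---|
| 0.05 | 2.55 | about 82% |
| 0.10 | 2.49 | about 84% |
| 0.20 | 2.34 | about 88% |

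In this balanced case the lost degrees of freedom cost under 0.5 point with 2 to 8 practices.

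**3. Simulated power.** 56 women; 2, 4 or 8 practices; half the women blocked by practice; plain t test against a REML random intercept:

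| ICC | t test | Random intercept |
|---|---|---|
| 0 | 80% | 80% |
| 0.05 | 80-81% | 81-82% |
| 0.10 | 81-83% | 84% |
| 0.20 | 81-85% | 86-88% |

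A separate simulation with 2, 4 or 7 practices gave a gain of about 0 to 2 points at ICC 0.05 to 0.10, 2 to 5 points at ICC 0.20, and no loss at ICC 0. Random-intercept type I error was about 3 to 6%.

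**4. Is the plain t test invalid?** Four practices, 6000 runs per setting, rejection rate with no true effect:

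| Allocation | ICC | t test | Fixed practice term |
|---|---|---|---|
| Not blocked | 0.10 | 5.2% | 4.8% |
| Not blocked | 0.20 | 4.9% | 5.0% |
| Blocked | 0.10 | 3.8% | 4.8% |
| Blocked | 0.20 | 3.3% | 4.9% |

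The t test is not inflated. If allocation is in fact blocked by practice, omitting the term makes the test conservative.

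**5. Chance imbalance.** Under simple 1:1 allocation, a practice with 8 women splits 6:2 or worse with probability 2 × (1 + 8 + 28)/256 = 0.29. Such splits are common, but the standard error already reflects them, as the unblocked rows in step 4 show.

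**6. Random or fixed practice effects.** With 8 practices, no blocking and ICC 0, fixed effects cost about 6 power points. The random intercept avoids that loss.

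None of these runs includes baseline pain. The documents give no correlation between baseline and later pain, so I put no figure on that term.

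**The case against.** The case against is substantial, and much of it stands.

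- **The t test sentence concerns sizing.** A reader might infer that the plan fixes a plain t test as the pain analysis. It does not; it names no post-baseline pain analysis at all. That is the larger gap, and it is why the fix starts there.
- **Several examiners are not established.** A reader might infer that every recruiting practice performs its own Q-tip test. Section 4 says where women come from, not where they are examined. Medical assistants share the examination, so practice and examiner need not coincide. With one examiner there is no examiner effect.
- **The primary score may be the diary.** No examiner's hand enters a self-rated diary. Practice case mix could still matter, but the technique argument would fall away. It gives no support for the other self-completed questionnaires either.
- **Unblocked allocation is not shown.** The documents are silent on the IVRS scheme. Blocking is unknown rather than absent.
- **Change from baseline would cancel a constant examiner shift.** True, but the plan does not say whether change or the raw score is analysed. Entering baseline pain in the model deals with part of the same problem.
- **The unadjusted test keeps its planned power.** In step 3 the t test never falls below 80%. This limits the point to an improvement. It does not remove the case for a term that costs nothing at ICC 0.

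**Conclusion.** The point holds as a conditional matter of precision. The plan draws women from several practices, leaves the primary pain comparison unwritten and has no practice term anywhere. If more than one practice scores women, a random practice intercept is worth 0 to about 5 power points for an ICC of 0 to 0.20, and nothing is lost at ICC 0. This rests on a total SD of 2.62, 2 to 8 equal practices and an assumed ICC, none of which the documents supply.

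Two stronger readings are not supported. One is that practice differences bias the result: under randomization, chance imbalance is random error, and the simulated type I error is not inflated. The other is that the trial falls short of 80% power. If 2.62 were the spread within a practice, the total SD would be 2.62/√(1 − ICC) = 2.69, 2.76 or 2.93 at ICC 0.05, 0.10 or 0.20, and the unadjusted t test would have about 78%, 76% or 71% power. The plan bases its sizing on earlier off-label use, so this cannot be excluded. But it states neither an SD nor which spread was used, so a shortfall is not shown.

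**What to change.** Before unblinding, add to Section 9:

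1. which rating is the primary pain score, Q-tip or diary;
2. that it is compared between arms by a linear model with arm, baseline pain and a random intercept for practice.

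Stating the number of practices and examiners would let a reader judge how much the term matters.

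The cost is a sentence or two of wording, with no extra women, visits or staff. The downsides are a slightly more complex model, a poorly estimated practice variance if there are only two practices, and no gain if practices do not differ or one examiner scores everyone.

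I would not change the allocation scheme mid-trial. The amendment shows that the trial is already enrolling, tubes come numbered from the compounding pharmacy, and the code may be broken for women who leave because of adverse reactions. Short blocks within practice could then make later assignments easier to guess. The analysis change does not depend on blocking.

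### Enrolling 64 covers 12.5% withdrawal, not the stated 15%: if 15% are lost to the primary comparison, about 54 remain instead of 56

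*Combined protocol and SAP*

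**What the plan says.** The Power Analyses part of Section 9 sets out the calculation in three steps.

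- **Design:** "Sample size was calculated to achieve at least 80% power with a significance level of 0.05 using a two-tailed, two-sample t test".
- **Number needed for analysis:** "A sample size of 56 subjects (28 subjects in treatment group and 28 subjects in the placebo group) was estimated to achieve 80% power" for a 2.0-point mean difference between arms on the 0–10 pain scale.
- **Number to enrol:** "To compensate for possible withdrawal of 15% of patients in the vulvodynia study, a total sample size of 64 participants" is required, split as 32 and 32.

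Section 4 (Subject Selection) repeats the enrolment figure: "64 women will be recruited from the practices of gynecologists and their colleagues".

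No SD is given. The only pointer to one is the statement that "The power analyses were based on previous research data on the effectiveness of the off label use of dilute Veregen" at 5% sinecatechins, with a patent as the source. The plan does not show how 56 became 64. It gives no other withdrawal rate, and it names no analysis set or missing-data rule that would keep withdrawn patients in the primary comparison.

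**The concern.** The withdrawal allowance exists so that 56 patients are still available for the comparison after the expected losses. The 15% is a share of the patients in the study, that is, of those enrolled. The enrolled number should therefore be the analysable number divided by 0.85. The stated 64 is smaller than that.

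What is at stake is mainly whether the justification agrees with itself. If withdrawal ran exactly at the planned 15%, the sponsor would report about 54 completers against a stated requirement of 56, although attrition had gone as planned. Anyone reading the protocol can find this with one division. A loss of power is the secondary question, and it is small.

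**Working it through.** **Inputs (Section 9, Power Analyses):** 56 needed (28 per arm), 15% withdrawal, 64 enrolled (32 per arm), two-sided two-sample t test at 0.05, difference 2.0 points, target power at least 80%.

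**Reproducing the plan's 64.** Adding 15% to the number needed gives 56 × 1.15 = 64.4 (28 × 1.15 = 32.2 per arm). Rounded to the nearest whole number, this is 64 (32 per arm). The stated figure is consistent with that shortcut, but the plan shows no working, so its origin is an inference.

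**What 64 delivers.**

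- Expected losses at 15%: 0.15 × 64 = 9.6.
- Expected remaining: 64 × 0.85 = 54.4, or 27.2 per arm.
- Losses that 64 can absorb: 64 − 56 = 8, and 8/64 = 12.5%.

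**What 15% requires.** N = 56/(1 − 0.15) = 65.9, rounded up to 66 (28/0.85 = 32.9, so 33 per arm). Check: 66 × 0.85 = 56.1. The next size down falls short: 65 × 0.85 = 55.25.

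**Effect on power.** The SD has to be assumed. The range used is the one for which 28 per arm is the smallest size reaching 80% power for 2.0 points. Solving the noncentral t power equation for the SD gives 2.623 for exactly 80% at 28 per arm and 2.574 for exactly 80% at 27 per arm.

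| Assumed SD | Power, 28 per arm | Power, 27 per arm | Difference detectable with 80% power, 27 per arm |
|---|---|---|---|
| 2.574 | 81.5% | 80.0% | 2.00 |
| 2.600 | 80.7% | 79.2% | not computed |
| 2.623 | 80.0% | 78.5% | 2.04 |

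Losing one patient per arm costs about 1.5 percentage points of power. Within this SD range, power ends between 78.5% and 80.0%.

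**The case against.** The strongest reply is that two participants do not matter. Section 9 presents its figures as preliminary estimates. One patient per arm is small beside the uncertainty in an unstated SD on which the 56 itself depends, and the loss against 80% may be zero. All of this stands, and it is why the point is minor. It does not make the sentence correct, because 65.9 does not round to 64.

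A second reply is that 64 is an ordinary approximation, 15% added to the number needed. That probably explains the figure. But the text speaks of 15% of patients withdrawing, and those counted in the 56 are by definition the ones who did not withdraw.

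A third reply is that withdrawn women may still contribute pain scores, since pain is recorded at several weeks and the plan has no analysis-set rule. The shortfall does depend on withdrawals being lost to the primary comparison. The plan's own inflation assumes this, since otherwise little or no inflation would be needed.

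A fourth reply concerns the power range, and it stands as a qualification. The range assumes an exact t-test calculation and equal losses in the two arms. If the sponsor used a normal approximation, the implied SD could be 2.67. The t-test power would then be 77.0% at 27 per arm, but most of that gap is already there at 28 per arm (78.6%). If the 54 were split 24 and 30, power would be 78.0% to 79.5% over the SD range in the table. The power figures are therefore illustrative. The counts of 54, 56 and 66 do not depend on the SD.

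**Conclusion.** The concern holds, as a minor error of arithmetic. On the plan's own numbers, 64 enrolled covers 12.5% withdrawal. At the stated 15% about 54 remain, two short of the 56 required, and meeting both figures takes 66. This rests on two readings: that 15% is a share of those enrolled, and that withdrawn patients are lost to the primary comparison. The wording and the plan's inflation support both.

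The cost in power is at most about 1.5 percentage points below the 80% target, and possibly nil, given an SD of 2.574 to 2.623, a t-test calculation and equal losses in the arms. It should not be presented as a material loss of power.

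**What to change.** Correct the withdrawal sentence in Section 9 in one of these ways.

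1. **Restate the allowance.** Say that 64 participants (32 per arm) allow for withdrawal of up to 12.5% (8 participants), leaving 56 (28 per arm). This changes one sentence and adds no patients. The sponsor should be content that 12.5% is a realistic expectation, because this option fits the allowance to the existing total.
2. **Keep 15% and report what it leaves.** Say that if 15% withdraw, about 54 of the 64 remain (27 per arm). Then give the power for 2.0 points at the SD actually used, and state that SD. On the back-solved range this is 78.5% to 80.0%. This also adds no patients, but the SD has to be disclosed.
3. **Keep both 15% and 56.** Enrol 66 (33 per arm). This adds two patients, and the total and per-arm figures in Section 9 and the recruitment figure in Section 4 must all change.

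Options 1 and 2 are enough to make the plan consistent.
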